8.3 Events of Clinical Interest

In addition to the above criteria, AEs meeting the following criteria (although not serious per ICH-GCP definition) are considered events of clinical interest. Any ECI occurring within the time period beginning when the consent form is signed until 100 days after the last dose of study treatment are reportable to the Sponsor in the same timeframe as an SAE, i.e. within 24 hours of the Investigator's knowledge of the event.

Events of clinical interest for this study include:

8.3.1 Hepatic toxicity

Hepatic toxicity of clinical interest is defined as an elevated ASAT or ALAT lab value \geq 3x ULN and an elevated total bilirubin lab value \geq 2x ULN and, at the same time, an alkaline phosphatase lab value \leq 2x the ULN, as determined by way of protocol-specified laboratory testing or unscheduled laboratory testing.

Note: These criteria are based upon available regulatory guidance documents. The purpose of the criteria is to specify a threshold of abnormal hepatic tests that may require an additional evaluation for an underlying etiology.

8.3.2 Pregnancy

The occurrence of pregnancy is not considered as an SAE. If, however a female study patient becomes pregnant or is discovered to have been pregnant during the treatment period or within 5 months after the last IP administration the investigator must immediately notify the Sponsor of this event via the Pregnancy Notification Form in accordance with SAE reporting procedures. Follow-up information regarding the course of the pregnancy, including perinatal and neonatal outcome and, where applicable, offspring information must be reported on the Pregnancy Notification Form.

Any pregnancy that occurs in a female partner of a male study patient during the treatment period or within 7 months after last IP administration should be reported to the Sponsor via the Pregnancy Notification Form. In order for Sponsor or designee to collect any pregnancy surveillance information from the female partner, the female partner must sign an informed consent form for disclosure of this information. Information on this pregnancy will be collected on the Pregnancy Notification Form.

Note: While pregnancy itself is not considered to be a SAE, any anomaly detected in the foetus or child, any elective termination of a pregnancy for medical reasons or spontaneous abortion will be reported as a SAE, using SAE reporting procedure (Section 8.2.3).

Protocol n° UC-0105/1612 - version n°10.0, November 22, 2021

9 ANCILLARY STUDY(IES)

9.1 Biological Ancillary Study

The aim of the proposed ancillary studies is to address specific scientific questions related to potential predictive biomarkers of efficacy and the mechanism of action of the antitumour immune response, such as:

- Which biomarkers are specifically associated with tumour response to treatment?
- Which biomarkers are specifically associated with treatment-related toxicity?
- What are the common immune parameters modified by the treatment in all patients?
- Which tumour immune infiltration patterns are seen in responding versus non-responding patients?
- Are identified biomarkers unique to a particular tumour, or universally present across all tumour types

9.1.1 Tumour Biopsy

Formalin-fixed, and paraffin-embedded biopsy samples of a metastatic site, or primitive tumour tissue are required from patients in order to perform retrospective immunohistochemistry analysis.

Archived samples will be collected in preference, however if suitable archived biopsy material is not available, a fresh biopsy of a tumour lesion may be performed following signature of the informed consent form and prior to the first administration of study treatment, unless this is medically contraindicated (e.g. site inaccessible or patient safety concerns).

Such biopsies should be performed by appropriately qualified personnel in accordance with clinical best practice and the local institutions standards of care. In addition, various measures are to be implemented to minimize the risk of the biopsy procedure, notably:

- Blood counts and hemostasis analysis will be performed prior to identify any coagulation abnormality which could prohibit a biopsy.
- Tumour lesions of more than 3 cm will be preferred to smaller lesions
- Non thoracic-lesions will be favored over pulmonary lesions to decrease the risk of biopsy

The site of biopsy will be selected by the Investigator according to accessibility and volume of metastatic tissue available. The choice of biopsy site and sampling conditions are to be reported in the eCRF.

Note: In the perspective of performing translational studies on biopsied tissue, the samples collected must be **core** biopsies; fine needle aspirations will not be accepted.

All biopsy samples will be shipped to the R&D UNICANCER Biological Resources Centre (Centre des Resources Biologiques) at the Centre Leon Berard (CRB-CLB, see Section 14.10).

Depending on the quality of tumour tissue collected, immunohistochemical staining will be performed according to the following order of priority:

- 1. PD-L1 expression in the tumour microenvironment
- 2. Tconv / Tregs (CD4+, FOXP3+) and CD8+ T cell infiltration and co-markers (Fas-L, OX40)
- 3. Tumour vascularization and markers of endothelium & pericytes (stainings for VEGF, CD31; CD34)
- 4. Macrophages (CD68/CD163 co-staining for M1/M2)
- 5. Dendritic Cells (DC-lamp, PS100)

In selected cases where exceptional responses or unexpected toxicities are observed additional biopsy samples of the tumour could be collected during the trial treatment for exploratory studies.

All biological specimens not used for genomic profiling will be stored centrally in the Unicancer Biobank located at the CRB-CLB.

9.1.2 Blood Samples

Blood samples (45 mL on heparin) will be collected for biomarker phenotyping and retrospective analyses during the Screening period and following treatment administration on Day 1 of Cycles 1, 2, 3, and 4. Additional samples are to be collected if the patient experiences a suspected immune-related toxicity.

Collected blood will be shipped to the CRB-CLB (see Section 14.10) for the following:

- Comprehensive blood phenotyping, notably costimulatory and co-inhibitory markers (ICOS, OX40, CTLA-4, PD-L1, CD137) and homing receptors (CLA) on T cells (Tregs & Tconv CD4+ T cells, CD8+ T-cells[CD8+/HLA-DR+/Ki-67+]) and NK cells.
- Serum storage for retrospective dosage of autoantibodies and antitumour antibodies.
- Plasma storage for retrospective dosage of circulating cytokines, chemokines and circulating receptors/ligands such as soluble PD-L1, soluble B7.1, soluble CD25, circulating levels of VEGFs, soluble VEGFRs, PDGF, FGF, ITAC, IL18, IL6, and IFNg.
- Plasma storage for subsequent ctDNA analysis and whole exome sequencing.

The procedure for blood processing and shipment are described in greater detail in a separate Laboratory Manual.

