Archived FFPE biopsy material obtained as part of the standard medical care (e.g. collected at time of diagnosis or relapse or prior surgical intervention) will be collected at study entry and shipped to the R&D UNICANCER Biological Resources Centre, at the Centre Leon Berard, Lyon, France. These tumour samples will be used to perform retrospective immunohistochemical staining to identify biomarkers related to the efficacy of pembrolizumab therapy.

Note: if suitable archived biopsy material is not available, a fresh biopsy of a tumour lesion may be requested, unless this is medically contraindicated.

In selected cases where exceptional responses or unexpected toxicities are observed additional biopsy samples of the tumour could be collected during the trial treatment for exploratory studies.

Blood samples will be collected prior to the first dose of IP (during the screening period) and following IP administration on Day 1 of Cycles 1, 2, 3 and 4. Additional samples may also be collected if the patient experiences a suspected immune-related toxicity.

SAMPLE QUANTITIES:

Forty-five millilitres (45 mL) of blood will be collected at each sampling time point.

G) TRIAL DURATIONS

INCLUSION PERIOD:

42 months

TREATMENT PERIOD:

Treatment will be continued for a maximum of 24 months (or 35 cycles, whichever is longer), or until disease progression. Treatment may also be terminated early at the initiative of either the patient or the investigator for any reason that would be beneficial to the patient, including: unacceptable toxicity, intercurrent conditions that preclude continuation of treatment, or patient request.

FOLLOW-LIP

12 months after the EoT visit of each patient.

For the patients rechallenged with pembrolizumab, the follow-up period may be extended of 1 year maximum.

DURATION UNTIL PRIMARY ENDPOINT EVALUATION:

The first stage will analyse data in each cohort independently of each other. Interim analysis of the ORR is planned after the 10 first patients eligible have been enrolled in the cohort and completed the first scheduled disease evaluation.

OVERALL TRIAL DURATION (INCLUDING FOLLOW-UP):

Approximately 6,5 years

Tumor Group UNICANCER: Immunotherapy Protocol n°: UC-0105/1612

EudraCT n°: 2016-002260-14

H) TRIAL FLOW-CHART

VISIT	PRE	SCR	C1D1	C2D1	C3D1	C4D1	C5D1	CnD1	EoT ⁽¹⁾	LTFU
Days		-28 - 0	D1	D22 (±2)	D43 (±2)	D64 (±2)	D85 (±2)	+Q 21 d (±2)		Q 90 d (±14)
Written informed consent		X								X ⁽³⁰⁾

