- o CT scan of the chest, abdomen and pelvis.
- o Detailed ophthalmologic examination with dilated fundus examination, slit-lamp examination and colour photography of the posterior pole.
- Lumbar puncture for central spinal fluid (CSF) cytology
- Verification of on-going corticosteroid treatment.
- Documentation of baseline tumour status including verification of all measurable (unidimensional measurements) and non-measurable lesions as per IPCG response criteria.

For patients with NK/T-cell lymphoma, disease assessment should include:

- Clinical assessment.
- Mandatory FDG-labelled PET-CT scan of the head, chest, abdomen, pelvis and extremities.
- o Documentation of baseline tumour status according to the 5-PS (Cheson, 2014)
- Lumbar puncture for central spinal fluid (CSF) cytology
- o Bone marrow biopsy or bone marrow aspiration

Note: same diagnostic method(s) must be used to evaluate disease status throughout the study. The results of all radiological assessment (DICOM format) must be provided on CD-ROM for central review by the IRC (Section 6.1.1).

- Verification of availability of a suitable FFPE biopsy sample of a metastatic site, or primitive tumour tissue. If suitable archived biopsy material is not available, a fresh biopsy of a tumour lesion may be performed following signature of the informed consent form and prior to the first administration of IP, unless this is medically contraindicated (Section 9.1.1)
- Collection of blood samples (45 mL on heparin) for phenotyping and retrospective analyses (see Section 9.1.2)

The following should be performed within 14 days prior to the first administration of study treatment:

- Electrocardiogram (12-lead)
- Haematology analysis including CD4+ count (see Table 5).
- Serum chemistry analysis (see Table 5).
- Measurement of coagulation factors: prothrombin time (PT)/International normalized ratio (INR), partial thromboplastin time (PTT) (see Table 5).
- Thyroid function tests: thyroid-stimulating hormone (TSH), total triiodothyronine (T3), free thyroxine (T4) (see Table 5).
- Patients with germ-cell cancer only: Measurement of biomarkers (AFP, hCG and LDH)
- Patients with NK/T-cell lymphoma only: PCR analysis of EBV load.
- Urinalysis (morning sample, fasting if possible): Blood, glucose, protein, specific gravity, microscopic examination of urinary sediment with concomitant dosing of creatinine (see Table 5).

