7.2.5 Subsequent Visits – Day 1 of Each Cycle

The following should be performed **prior to administration** of IP on Day 1 of every cycle:

- Complete clinical examination (major body systems)
- Measurement of vital signs (blood pressure, seated heart rate, body temperature)
- Assessment of ECOG performance status
- · Assessment of ongoing toxicities.
- Haematology⁴ analysis (see Table 5).
- Serum chemistry⁴ (see Table 5).
- Patients with germ-cell cancer only: Measurement of biomarkers (AFP, hCG and LDH)⁴

If the patient experiences a suspected immune-related toxicity a blood sample (45 mL on heparin) should also be collected for phenotyping and retrospective analyses (see Section 9.1.2)

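### The whole 45 mL research draw is put on heparin, so the serum that Section 9.1.2 says will be stored from it cannot be obtained as written

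*Protocol*

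**What the plan says.** Section 9.1.2 of the protocol fixes the research draw: "Blood samples (45 mL on heparin) will be collected for biomarker phenotyping and retrospective analyses". It schedules this draw once at screening and again after dosing on Day 1 of Cycles 1 to 4. Section 7.1 gives the same instruction to sites: "Collection of blood samples (45 mL on heparin) for phenotyping and retrospective analyses". Sections 7.2.1 to 7.2.4 repeat it for Cycles 1 to 4. For a suspected immune-related toxicity, Section 7.2.5 asks that "a blood sample (45 mL on heparin) should also be collected for phenotyping and retrospective analyses".

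The synopsis (section F, sample quantities) gives the volume: "Forty-five millilitres (45 mL) of blood will be collected at each sampling time point".

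Section 9.1.2 then lists four uses of the collected blood. The first is cell phenotyping. The other three are:
- for the antibody work: "Serum storage for retrospective dosage of autoantibodies and antitumour antibodies"
- for the soluble markers, of which more are named than are quoted here: "Plasma storage for retrospective dosage of circulating cytokines, chemokines and circulating receptors/ligands such as soluble PD-L1"
- for the sequencing work: "Plasma storage for subsequent ctDNA analysis and whole exome sequencing"

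Serum for antibodies and plasma for soluble factors are also named as separate materials in the synopsis methodology, Section 1.3.1, Section 3.2 and Section 14.10.2. Section 9.1.2 closes by referring to a separate Laboratory Manual for blood processing and shipment.

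**The concern.** The tube and the intended use do not fit each other. Serum is the fluid left once blood has clotted, and heparin is added to stop clotting. A heparin tube can be spun for plasma or used for cells, but it does not give serum. If the whole draw is on heparin, one of the four listed uses has no material to work on.

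The ancillary objective (Section 2.3) is to find molecular mechanisms that separate responders from non-responders within a cohort, and Section 14.10.2 names antibody measurement in serum as part of that analysis. The samples are tied to screening and to the first four cycles. A tube error found later cannot be put right by drawing again, because the pre-treatment and early on-treatment states have passed. Patients would also be giving research blood under an instruction that cannot deliver one of its stated purposes.

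**Working it through.** The protocol states no statistical figure on this point, so the check is a comparison of texts with one subtraction.

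**Step 1: which tube is named?** Every place that names a tube for this blood says heparin:

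| Place in the protocol | Time point | Tube and volume |
|---|---|---|
| 7.1 | Screening | 45 mL, heparin |
| 7.2.1 to 7.2.4 | Day 1 of Cycles 1, 2, 3 and 4 | 45 mL, heparin |
| 7.2.5 | Suspected immune-related toxicity | 45 mL, heparin |
| 9.1.2 | Summary of all the above | 45 mL, heparin |
| Synopsis F | Each sampling time point | 45 mL, tube not named |

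The synopsis methodology, flow-chart footnote 28 and Sections 3.2 and 14.10.2 describe the samples without naming a tube. No place mentions a clot tube, an EDTA tube or a cell-free-DNA tube.

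**Step 2: is any blood left outside heparin?** Total per time point (Synopsis F) minus volume on heparin (7.1, 7.2.1 to 7.2.5, 9.1.2): 45 − 45 = 0 mL. The scheduled draws are screening plus four cycles, so 5 × 45 = 225 mL per patient who completes them, all on heparin as written.

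**Step 3: can each listed use be met from heparin blood?**

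| Use in 9.1.2 | Material needed | Available from a heparin draw? |
|---|---|---|
| Cell phenotyping | Cells | Yes |
| Autoantibodies, antitumour antibodies | Serum | No |
| Cytokines, chemokines, soluble receptors and ligands | Plasma | Yes |
| ctDNA and exome sequencing | Plasma | Yes as a material; suitability is a separate query |

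**Step 4: could serum be loose wording for plasma?** That is unlikely. Section 9.1.2 gives serum and plasma separate lines with different assays, and the other four places listed above keep the same distinction.

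**Step 5: does the Laboratory Manual resolve it?** The reference to the manual covers processing and shipment and does not mention the tube. If the manual does provide a serum tube, then either less than 45 mL goes on heparin, which contradicts Sections 7 and 9.1.2, or more than 45 mL is drawn, which contradicts Synopsis F. The protocol text needs correction in either case.

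**The case against.** The strongest reply is that the heparin phrase is one piece of shorthand copied into several sections, while other descriptions of the same samples name no tube and expressly expect both serum and plasma. The Laboratory Manual and the kits, which are not shown, may already supply a serum tube. This stands as far as it goes: the documents do not show what sites actually drew, so actual loss of serum is not established. It does not rescue the wording, because the visit sections are the instructions that sites follow and they fix both tube and volume.

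Three stronger readings are tempting, and the documents do not support them.

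- **That the sequencing line is also contradicted.** A reader might infer this because heparin is often regarded as a poor choice before amplification. The protocol asks for plasma, and heparin blood gives plasma, so the text does not conflict. Whether heparin matters is a question of degree. It rests on general laboratory knowledge and depends on processing steps in the unseen manual, so it warrants only a query.
- **That the antibody work is lost.** The text shows that serum cannot be stored as written. It does not show that these antibodies could not be measured in heparin plasma and reported as such.
- **That the loss can be counted in draws.** 350 patients × 5 draws = 1,750 draws, and 1,750 × 45 mL = 78.75 L. This is a ceiling on blood drawn, assuming that every patient reaches Cycle 4. It does not measure information lost.

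It is also fair to say that this is ancillary, retrospective research. The tissue staining in Section 9.1.1 is unaffected.

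**Conclusion.** The point holds as an internal contradiction. As written, one of the four uses in Section 9.1.2, serum storage, has no blood to draw on: 0 of 45 mL at every time point. The other three uses can be supplied from heparin blood, subject to the query on sequencing.

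The conclusion rests on two assumptions: that 45 mL in Synopsis F is the full research volume per time point, as its wording indicates, and that serum is meant in its ordinary sense. It does not depend on what the Laboratory Manual contains. How much harm has followed does depend on that, and on the tubes actually used, neither of which can be seen here.

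The reach is limited to the ancillary biomarker research. The primary endpoint (Section 3.1.1), the sample size (Section 10.1) and the stopping rules (Section 10.3) do not use these samples. It should be corrected because the instruction is repeated at every visit and the samples cannot be retaken.

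**What to change.** In Sections 7.1, 7.2.1 to 7.2.5 and 9.1.2, replace the statement that all 45 mL is on heparin with a stated split of the same 45 mL. The split should include a tube without anticoagulant for serum, with the remainder anticoagulated for phenotyping and plasma. The sponsor's laboratory should set the volumes, since the protocol gives no volume requirement for any assay. Align Synopsis F and the Laboratory Manual with the split.

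For samples already taken, establish from the kit and biobank records which tubes were drawn. Report any antibody assay run on heparin blood as a heparin-plasma assay and not as a serum assay.

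As a secondary query, ask the laboratory to confirm that the anticoagulant suits the planned ctDNA and exome assays, for example whether an EDTA or cell-stabilising tube is needed for that portion.

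The cost is revised wording in the protocol and manual, a different tube set in the kit, and somewhat less blood for phenotyping. No extra blood volume or visit is needed.

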10 STATISTICAL ANALYSIS PLAN

10.1 Required Number of Patients

This is a Phase 2, non-randomised, open-label, multicentric study to investigate the efficacy and safety of pembrolizumab monotherapy in patients with specific rare cancers who have unresectable locally advanced or metastatic disease, which is resistant or refractory to standard therapy, or for which standard therapy does not exist, or is not considered appropriate, and for which no other experimental treatment options are available. The trial is designed to identify subsets of patients that may benefit from treatment.

Enrolled patients will be assigned to cohorts based on disease indication. Seven cohorts are defined as follows:

- Cohort 1: Rare sarcoma
- Cohort 2: Rare ovarian cancer
- Cohort 3: Primary central nervous system lymphomas
- Cohort 4: Rare thyroid cancer
- Cohort 5: Rare malignant neuroendocrine cancer
- Cohort 6: Germ-cell cancer
- Cohort 7: NK/T-cell lymphoma

This will be an adaptive design since new cohorts may be defined by the Steering Committee during the course of the trial (see Section 11.3).

The study plans to enrol 350 patients in to one of 7 cohorts. In total between 20 and 50 patients will be enrolled in each cohort, with the exception of the cohort 1 for which up to 80 patients may be enrolled (extension introduced under amendment 5 of this protocol). Following the amendment 6, up to a maximum of 50 additional patients may be included in the Sarcoma (cohort 1), Rare ovarian cancer (cohort 2) or Primary central nervous system lymphoma (cohort 3) cohorts, within the limit of 350 patients to be included in total.

Patient enrolment to individual cohorts will continue until the stopping rules applied at each interim analysis are met, or until the maximum sample size is reached.

Based on the number of investigational centres and the expected accrual rate for patients with the appropriate profile, i.e. 10-15 patients per cohort per year, patient enrolment is expected to be complete in 3.5 years.

The final analysis is scheduled for approximately 4 years after the last patient is enrolled.

10.2 Planned Statistical Analysis

The trial will use a two-stage Bayesian enrichment design, allowing for a smaller more informative trial that is specifically tied to decision making within a drug development program. This process allows for incremental changes to each cohort based on current data, rather than restricting revisions in a trial design using fixed sample sizes.

The first stage treats all patients from the different cohorts with the IP and identifies possibly sensitive subpopulations (Berry 2013). The second stage will compare response rates across subsets within the selected cohorts (Trippa 2012).

Let p0, define the rate of response that is considered uninteresting, and p1 a targeted level of interest. Let k, be the number of initially defined cohorts of patients. Let Y=0,1 define the response of patient I in the cohort k, and nki the total sample size.

We will model the probability of response, $\theta = P(Y=1)$, and will use a subscript to indicate patient cohort: $\theta_1, \theta_2, ... \theta_k$. This allows us to reflect the treatment effects in each group relatively to the targeted values. All inference and stopping rules on futility or efficacy will be based on the probability scale which is clinically interpretable (Berry 2013; Jacob 2016, Zalavsky 2013).

The first stage will analyse data in each cohort independently of the other cohorts. Interim analysis of the primary endpoint (ORR according to Investigator response assessment) is planned after the 10 first patients eligible have been enrolled in the cohort and completed the first scheduled disease evaluation.

Based on the estimated response rate and its posterior distribution in each cohort, cohorts that do not reach a targeted level of confidence in terms of minimal efficacy will be potentially closed to further recruitment.

In the second stage intra-cohort analyses will be performed after every 5 additional patients accrued (Berry 2013). These analyses will use all data accumulated up to that point, and will consider potential predictive markers of efficacy; such subsets analyses will result in potentially sub-cohorts of poor outcomes that may be proposed for enrolment discontinuation while those of good outcomes will enrich the design (Mandrekar 2009; Zang 2016).

In the absence of a decision to halt enrolment, accrual in each cohort will continue until the end of the planned of recruitment period (3 years after activation of the first site) or a maximal accrual of 50 patients is achieved (whatever occurs first). In case of promising subtypes, enrolment could increase possibly above the pre-established limit of 50 patients, unless the maximal sample size of 350 patients has been reached or the termination date of study enrolment. There is no drawback from a statistical point of view that sample size of cohorts will differ from one another, while increased subsamples may allow more accurate estimates of the outcome in those subsets.

Note: Patient enrolment will be suspended for each cohort following the inclusion of the 10 first patients eligible until the outcome of the interim analysis is known. Enrolment may be reopened prior to the interim analysis upon the decision of the Steering Committee if there is a recognised clinical need and provided that at least one response has been observed and confirmed by a collegiate revue.

Rare ovarian cancer cohort: due to the aggressively of this disease and the prognostic heterogeneity between ovarian cancer subtypes with the difficulties this poses in the interpretation of response rate, the decision to continue enrolment in this cohort will also take into account the number of patients with stabilisation of their disease. Recruitment to this cohort will continue (up to 50 patients) if $\geq 4/10$ patients achieve at least stable disease at their first disease evaluation. Response rate will be subsequently reevaluated for each histological subset following the inclusion of the 10 first patients of each type with the application of the stopping rule as outlined below. In the subset of promising subtypes (teratoma and low-grade serous carcinoma), enrolment will increase possibly above the pre-established limit of 50 patients.

Final analysis of efficacy endpoints will be performed using both the Investigator and IRC assessment of response according to RECIST v1.1, or RECIST v1.1 combined with biomarker assessment, or IPCG response criteria, or the 'Lugano' response using the FDG-PET-CT 5-PS and assessment of EBV load. Comparisons between Investigator and IRC results will also be reported.

Statistical data will be expressed in the form of:

- Frequencies and Percentages (qualitative variables),
- Mean and standard deviation
- Median and interquartile range (quantitative variables),
- Survival curve estimates calculated with the Kaplan Meier method (survival data) (Kaplan, 1958).

Each primary and secondary evaluation criterion will be reported with a confidence interval of 95%.

Multivariate predictive analyses of each endpoint will be performed with regression models: logistic regression (for the main end point), and Cox (for PFS and OS) models.

Gail and Simon statistics will be used to test if the disease features and the mutational load measured in tumour samples of certain cohorts is correlated with pembrolizumab efficacy on the primary end point.

Data will be analysed with the SAS (SAS Inc, Cary, NC) and R (https://www.R-project.org/) software packages

